9.5.4.3 Reporting of Events Associated with Special Situations

9.5.4.3.1 REPORTING OF ADVERSE EVENTS ASSOCIATED WITH STUDY DRUG OVERDOSE, MISUSE, ABUSE, OR MEDICATION ERROR

Adverse events associated with study drug overdose, misuse, abuse, and medication error refer to AEs associated with uses of the study drug outside of that specified by the protocol. Overdose, misuse, abuse, and medication error are defined as follows:

| | |
|------------------|--|
| Overdose | Accidental or intentional use of the study drug in an amount higher than the protocol-defined dose |
| Misuse | Intentional and inappropriate use of study drug not in accordance with the protocol |
| Abuse | Sporadic or persistent intentional excessive use of study drug accompanied by harmful physical or psychological effects |
| Medication error | Any unintentional event that causes or leads to inappropriate study drug use or subject harm while the study drug is in the control of site personnel or the subject |

All AEs associated with overdose, misuse, abuse, or medication error should be captured on the Adverse Event eCRF and also reported using the procedures detailed in Reporting of Serious Adverse Events ([Section 9.5.4.1](#)) even if the AEs do not meet serious criteria. Abuse is always to be captured as an AE. If the AE associated with an overdose, misuse, abuse, or medication error does not meet serious criteria, it must still be reported using the SAE form and in an expedited manner but should be noted as nonserious on the SAE form and the Adverse Event eCRF.

9.5.4.3.2 REPORTING OF STUDY-SPECIFIC EVENTS

Study-specific events (as detailed in [Section 9.5.1.5.2](#)) should always be considered serious important medical events and be entered on the Adverse Event eCRF and reported using the procedures detailed in Reporting of Serious Adverse Events ([Section 9.5.4.1](#)), even if the study-specific event does not meet other serious criteria.

9.5.4.4 Expedited Reporting

The sponsor must inform investigators (or as regionally required, the head of the medical institution) and regulatory authorities of reportable events, in compliance with applicable regulatory requirements, on an expedited basis (ie, within specific time frames). For this reason, it is imperative that sites provide complete SAE information in the manner described above.

9.5.4.5 Breaking the Blind

In the case of a medical emergency where the appropriate treatment of the subject requires knowledge of the study treatment given, the investigator may break the randomization code for an individual subject. In all such cases, the AE necessitating the emergency blind break will be handled as an SAE in accordance with the procedures indicated above. Any broken code will be clearly justified and documented. The medical monitor must be notified immediately of the blind break.

9.5.4.6 Regulatory Reporting of Adverse Events

Adverse events will be reported by the sponsor or a third party acting on behalf of the sponsor to regulatory authorities in compliance with local and regional law and established guidance. The format of these reports will be dictated by the local and regional requirements.

All studies that are conducted within any European country will comply with European GCP Directive 2005/28/EC and Clinical Trial Directive 2001/20/EC. All SUSARs will be reported, as required, to the competent authorities of all involved European member states.

9.5.5 Completion/Discontinuation of Subjects

A subject may elect to discontinue study drug or withdraw from the study at any time for any reason. All subjects who discontinue taking study drug prematurely for any reason will undergo an ED Visit within 7 days of their last dose of study drug (see [Section 9.1.2.2](#)). In addition, Follow-Up Visits will be scheduled 2, 4, 8, and 12 weeks after the last dose of study drug (Visits W2, 19, W8, and Visit 20, respectively) (see [Section 9.1.2.3](#)). (revised per Amendment 04) See [Table 7](#) for full details of the assessments to be performed at these visits. revised per Amendment 05) Subjects who discontinue study drug early (as opposed to subjects whose dosing with study drug is temporarily suspended under Medical Monitor guidance) will not be permitted to restart study drug.

The investigator will promptly explain to the subject involved that the study will be discontinued for that subject and will provide appropriate medical treatment and other necessary measures for the subject. A subject who has ceased to return for visits will be followed up by mail, phone, or other means to gather information such as the reason for failure to return, the status of treatment compliance, the presence or absence of AEs, and clinical courses of signs and symptoms.

Subjects who withdraw prematurely from the study will be withdrawn for 1 of these primary reasons: AE(s), lost to follow-up, subject choice, inadequate therapeutic effect, withdrawal of consent, pregnancy, study terminated by sponsor, or other. In addition to the primary reason, the subject may indicate 1 or more secondary reason(s) for withdrawal from the study. Study disposition information will be collected on the Subject Disposition eCRF.

A subject removed from the study for any reason may not be replaced.

9.5.6 Abuse or Diversion of Study Drug

Adverse events associated with abuse or diversion will be appropriately reported as AEs and monitored per [Section 9.5.1.5.1](#). Abuse is always to be captured as an AE.

During the study, the investigator should be aware of the possibility of abuse or diversion of study drugs and should report any concern about mishandling, abuse, loss, theft, or diversion of study drugs by completing the Abuse or Diversion of Study Drug eCRF. (revised per Amendment 04)

9.5.7 Confirmation of Medical Care by Another Physician

The investigator will instruct subjects to inform site personnel when they are planning to receive medical care by another physician. At each visit, the investigator will ask the subject whether he or she has received medical care by another physician since the last visit or is planning to do so in the future. When the subject is going to receive medical care by another physician, the investigator, with the consent of the subject, will inform the other physician that the subject is participating in the clinical study.

9.6 Data Quality Assurance

This study will be organized, performed, and reported in compliance with the protocol, standard operating procedures, working practice documents, and applicable regulations and guidelines. Site audits will be made periodically by the sponsor's or the CRO's qualified compliance auditing team, which is an independent function from the study team responsible for conduct of the study.

9.6.1 Data Collection

Data required by the protocol will be collected on the eCRFs and entered into a validated data management system that is compliant with all regulatory requirements. As defined by ICH guidelines, the CRF is a printed, optical, or electronic document designed to record all of the protocol-required information to be reported to the sponsor on each study subject.

Data collection on the eCRF must follow the instructions described in the CRF Completion Guidelines. The investigator has ultimate responsibility for the collection and reporting of all clinical data entered on the eCRF. The investigator or designee as identified on Form FDA 1572 (where applicable) must sign the completed eCRF to attest to its accuracy, authenticity, and completeness.

Completed, original eCRFs are the sole property of Eisai and should not be made available in any form to third parties without written permission from Eisai, except for authorized representatives of Eisai or appropriate regulatory authorities.

9.6.2 Clinical Data Management

All software applications used in the collection of data will be properly validated following standard computer system validation that is compliant with all regulatory requirements. All data, both eCRF and external data (eg, laboratory data), will be entered into a clinical system.

Electronic source (eSource) methodology may be used for some of the clinical efficacy assessments performed in this study.

9.7 Statistical Methods

All statistical analyses will be performed by the sponsor or designee. Statistical analyses will be performed using SAS software or other validated statistical software as required.

All statistical tests will be based on the 5% (2-sided) level of significance. (revised per Amendment 05)

9.7.1 Statistical and Analytical Plans

The statistical analyses of study data are described in this section. Analyses will be performed based on treatment group, which will be defined in the statistical analysis plan (SAP). Additional analyses related to dose re-assignment will be performed for subjects who will be switched from E2609 5 mg and 15 mg to E2609 50 mg. Further details will be provided in the SAP, which will be finalized before database lock. (revised per Amendment 06)

9.7.1.1 Study Endpoints

9.7.1.1.1 PRIMARY ENDPOINT

- Safety and tolerability, which include incidence of TEAEs and SAEs, laboratory parameters, vital signs, and ECG parameters (revised per Amendment 05)

9.7.1.1.2 SECONDARY ENDPOINTS

(revised per Amendments 02 and 05)

- % reduction of A β (1-x) and A β (1-42) in CSF relative to baseline after from 4 weeks and up to 18 months of treatment
- The population PK parameters of E2609 in CSF and plasma, including the effect of intrinsic and extrinsic factors (including NAT2 phenotype)

9.7.1.1.3 EXPLORATORY ENDPOINTS

(revised per Amendments 01, 02, 04, and 05)

Change from baseline in:

- CSF A β (1-40) and BACE1 variables (eg, activity and protein levels) after at least 4 weeks and at 18 months of treatment
- CSF biomarkers of neurodegeneration (eg, t-tau and p-tau) at 18 months of treatment
- Plasma amyloid measurements from 4 weeks and up to 18 months of treatment, and during posttreatment follow-up
- CSF amyloid and CSF BACE1 measurements after 4 weeks and 18 months of treatment (revised per Amendment 06)
- Total hippocampal volume at 12 and 18 months of treatment as measured by vMRI
- Left and right hippocampal, whole brain, and total ventricular volume at 6, 12, and 18 months of treatment as measured by vMRI
- Amyloid PET standardized uptake value ratio (SUVR) composite at 18 months for brain amyloid levels as measured
- The following clinical assessments at 12 weeks and at 6, 9, 12, 15, 18, 19, and 21 months: ADAS-cog₁₄, CDR, MMSE, ISLT, CBB, and FAQ

9.7.1.2 Definitions of Analysis Sets

- The Randomized Set is the group of subjects who are randomized to study drug.
- The Safety Analysis Set is the group of subjects who receive at least 1 dose of study drug and have at least 1 postdose safety assessment.
- The Full Analysis Set (FAS) is the group of randomized subjects who receive at least 1 dose of study drug and have baseline and at least 1 postdose exploratory efficacy measurement. (revised per Amendment 05)
- The PK Analysis Set is the group of subjects with at least 1 quantifiable E2609 plasma concentration accompanied by a documented dosing history.
- The PD Analysis Set is the group of subjects who have a baseline PD measurement and at least 1 posttreatment PD measurement.

9.7.1.3 Subject Disposition

The number of subjects screened, the number (percent) of subjects who failed screening, and the reasons for screen failure will be summarized, based on data reported on the Screening Disposition eCRF. The number of randomized subjects enrolled at each site will be summarized by treatment group. The primary reasons for screen failures (did not meet inclusion or met exclusion criteria, AE, lost to follow-up, withdrawal of consent, and other) will be presented.

Study Completion: The number (percent) of randomized and treated subjects who completed the study and who withdrew from the study will be summarized according to the primary reason for discontinuation and secondary reason(s) for discontinuation, based on data reported on the Subject Disposition (Study Phase) CRF. The number (percent) will be presented by treatment group and total for subjects; randomized, not treated, treated, who completed the study, and withdrew from the study. The primary reasons for discontinuation from the study are: AE, lost to follow-up, subject choice, withdrawal of consent, pregnancy, study terminated by sponsor, and other. The secondary reasons for discontinuation from the study are: AE, subject choice, and other.

Completion of Study Treatment: The number (percent) of randomized and treated subjects who completed study drug and who discontinued from study drug will be summarized according to the primary reason for discontinuation and also according to secondary reason(s) for discontinuation, based on data reported on both the Subject Disposition (Study Phase) eCRF and ED from Study Drug eCRF. The number (percent) will be presented by treatment group and total for subjects; randomized, not treated, treated, who completed study drug, and discontinued from study drug. The primary reasons for discontinuation from the study drug are: AE, lost to follow-up, subject choice, withdrawal of consent, pregnancy, study terminated by sponsor, inadequate therapeutic response, and other. The secondary reasons for discontinuation from the study are: AE, subject choice, and other.

9.7.1.4 Demographic and Other Baseline Characteristics

Demographic and other baseline characteristics for the Safety Analysis Set and FAS will be summarized by treatment group using descriptive statistics. Continuous demographic and baseline variables include age, MMSE and FAQ; categorical variables include sex, age group (≤ 65 years, age > 65 years), race, ethnicity, *ApoE4* status (positive or negative), prior treatment with AChEIs or memantine (no or yes), and clinical population (MCI/Prodromal AD or mild to moderate AD). (revised per Amendment 01)

9.7.1.5 Prior and Concomitant Therapy

All investigator terms for medications recorded in the eCRF will be coded to an 11-digit code using the World Health Organization Drug Dictionary (WHO DD) (Mar 2014 or higher). (revised per Amendment 04) The number (percentage) of subjects who took prior and concomitant medications will be summarized on the Safety Analysis Set by treatment group, Anatomical Therapeutic Chemical class, and WHO DD preferred term. Prior medications will be defined as medications that stopped before the first dose of study drug. Concomitant medications will be defined as medications that (1) started before the first dose of study drug and were continuing at the time of the first dose of study drug, or (2) started on or after the date of the first dose of study drug up to the date of the last dose. All medications will be presented in subject data listings.

Medications taken within the 12-week Follow-Up period will also be recorded.

9.7.1.6 Efficacy and Biomarker Analyses (revised per Amendment 05)

9.7.1.6.1 PRIMARY EFFICACY ANALYSIS

There is no primary efficacy endpoint. (revised per Amendment 05)

9.7.1.6.2 SECONDARY EFFICACY ANALYSES

An mixed-effects model with repeated measures (MMRM) will be used to analyze the following secondary endpoint:

- Change from baseline in CSF A β (1-x) and CSF A β (1-42) from 4 weeks and up to 18 months. Data from early discontinuations will also be included. (revised per Amendment 05)

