| Randomization | X | | | | | | | | | | | | | | | | | | | | | | | | | | |
| Dispense study drug ^x | X | X | X | X | X | X | X | X | X | X | X | X | X | X | X | X | | | | | | | | | | | |

Footnotes for Table 7

ADAS-cog₁₄ = Alzheimer's Disease Assessment Scale - Cognitive subscale (14 items), CBB = CogState Brief Battery, CBP = childbearing potential, CDR = Clinical Dementia Rating scale, CSF = cerebrospinal fluid, C-SSRS = Columbia Suicide Severity Rating Scale, ECG = electrocardiogram, ED = Early Discontinuation, FAQ = Functional Assessment Questionnaire (also known as the Functional Activities Questionnaire), Ig = immunoglobulin, ISLT = International Shopping List Task, LP = lumbar puncture, MMSE = Mini Mental State Examination, MRI = magnetic resonance imaging, PBMC = peripheral blood mononuclear cell, PD = pharmacodynamics, PET = positron emission tomography, PK = pharmacokinetics, UNS = unscheduled, W2 = new Week 2 follow-up visit, W8 = new Week 8 follow-up visit. (revised per Amendment 04)

- a: Visit 3 should be conducted no more than 10 days after completion of the Baseline visit (Visit 2) assessments and confirmation of eligibility to continue in the study, unless additional time is required to take Exclusion Criterion #20 into account. (revised per Amendment 02) A window of ± 3 days will be permitted for Visit 4 to 14 inclusive. A window of ± 10 days will be permitted for Visit 15 to 18 inclusive. A window of ± 3 days will be permitted for the Follow-Up Visits. If use is made of the permitted visit windows, every effort should be made to bring the subject back in line with the "weeks elapsed since first dose" at subsequent visits.
- b: Subjects who discontinue taking study drug prematurely for any reason will undergo an ED Visit within 7 days of their last dose of study drug. In addition, Follow-Up Visits will be scheduled 2, 4, 8, and 12 weeks after the last dose of study drug (Visit W2, 19, W8, and Visit 20, respectively). (revised per Amendments 04 and 05)
- c: All subjects, regardless of whether they complete all 18 months of treatment or discontinue study drug prematurely, will complete 4 post-treatment Follow-Up visits; 2, 4, 8, and 12 weeks after the last dose of study drug (Visits W2, 19, W8, and 20, respectively). If clinically indicated, more frequent safety assessments can be made as UNS assessments or visits during the post-treatment Follow-Up period. (revised per Amendment 04)

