- v: For subjects who consent to CSF sample collection: Postrandomization CSF sample collection is scheduled at Visit 7 (or later postrandomization timepoint) and Visit 18/ED. If a postrandomization CSF sample is collected later than Visit 7, time-matched plasma PK samples are also required (see Footnote t). All visits at which CSF samples are scheduled to be taken also include blood PK and PD assessments and so the subject will be dosed at the clinic on these days. The timing of the Baseline LP needs to be scheduled carefully such that subsequent LPs (Visit 7 [or later postrandomization timepoint] and Visit 18) can be performed between 4 and 8 hours postdose and at a similar time of day (± 1 hour) for each individual subject. The CSF sample will be taken with the subject fasting (preferred) or at least 2 hours after the most recent meal. A gravity drip collection method must be used. If the LP and the cognitive tests are performed on the same day, the LP must be performed after the cognitive tests have been completed and the subject should rest and drink some fluid to hydrate before the LP. Subjects will be encouraged to stay at the site after completion of LP for medical observation. The CSF sample will not be taken at the ED Visit if this visit occurs within 3 months of a previous CSF sample. If at an ED Visit, the subject has already

Footnotes for Table 7

stopped study drug, then no dosing will take place, but the CSF sample will still be collected unless it was already collected within the past 3 months. . Subjects who initially consented to CSF collection and provided a baseline CSF sample but did not provide a postrandomization sample will be approached to consider reconsenting to postrandomization CSF sample collection even if they are beyond Week 5 (Visit 7); however, subject re-consent to this procedure is optional for these subjects. (revised per Amendments 01, 02, and 04)

- w: Subjects reporting AEs relating to abnormal dreams, nightmares, or sleep terror will be questioned on the frequency and impact of these events.
- x: The first dose of study drug will be given to the subject at the study site and the subject will be encouraged to stay at the site for an appropriate period of time as determined by the PI or Safety Physician for postdose medical observation. (revised per Amendment 02)

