This study will be limited to approximately 35 sites in the United States, with approximately 60 ($\pm 20\%$) eligible subjects randomized at Visit 3, 1:1:1:1 to 4 treatment groups within each clinical cohort. In addition to the placebo group, 3 doses of E2609 will be used to reduce CSF A β levels by approximately 25% (5 mg), 50% (15 mg), and 75% (50 mg) from baseline, respectively, at steady state. PK/PD modeling shows these doses should achieve these targets when administered QD with food and will be evaluated based on the 4-week (or later) assessment of CSF A β (1-x) from subjects who provide voluntary consent for CSF measurement (see [Section 9.4.4](#)). (revised per Amendments 01, 02, 04, and 05) Safety data will be monitored in a blinded fashion on a regular basis. In addition, approximately every 3 months from the time the 1st subject is randomized into the study, an independent DSMB (including at least 1 immunologist) will review all safety data in an unblinded manner. The DSMB will make recommendations to Eisai after each review as to whether any change(s) to the study are necessary. (revised per Amendments 01, 04, and 05)

Subjects who initially consented to CSF collection and provided a baseline CSF sample but did not provide a postrandomization sample will be approached to consider reconsenting to postrandomization CSF sample collection even if they are beyond Week 5 (Visit 7); however, subject re-consent to this procedure is optional for these subjects. (revised per Amendment 04)

Interim analyses of the E2609 plasma PK for all subjects and the E2609 CSF PK and PD profiles will be performed on baseline data and samples collected after at least 4 weeks of treatment. (revised per Amendment 05) Refer [Section 9.7.3](#) for more detail. These data will be used to evaluate the CSF PD effects of E2609 doses, where PD is measured as reductions from baseline in CSF A β (1-x) levels (see [Section 9.4.4](#)). The median and mean percentage

change from baseline in CSF A β (1-x) measured after 4 weeks or more of treatment for each dose of E2609 and the 90% confidence interval (CI) for the median will be derived. In addition, exploratory PK/PD modeling will be conducted. This PK/PD modeling will use the observed PK and PD data and will relate the average steady state plasma concentration of E2609 to steady state CSF A β (1-x) percentage reduction from baseline determined after at least 4 weeks of dosing. (revised per Amendments 01, 02, 03, and 04)

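### The CSF amyloid MMRM takes in early-discontinuation samples with no on-treatment limit, so off-drug values can pull the active-arm reductions toward zero

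*Protocol*

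**What the plan says.** Section 9.7.1.1.2 defines the secondary endpoint as the percentage reduction of Aβ(1-x) and Aβ(1-42) "in CSF relative to baseline after from 4 weeks and up to 18 months of treatment". Section 9.1 describes the three doses by the CSF reduction they should reach "from baseline, respectively, at steady state".

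Table 7 footnote v schedules the Baseline lumbar puncture (LP) so that the later ones, at Visit 7 (or later) and Visit 18, "can be performed between 4 and 8 hours postdose and at a similar time of day".

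Early discontinuation is handled differently. Under Table 7 footnote b, a subject who stops early "will undergo an ED Visit within 7 days of their last dose of study drug". Under footnote v, if drug has already been stopped by then, "then no dosing will take place, but the CSF sample will still be collected unless it was already collected within the past 3 months".

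Section 9.7.1.6.2 then sets the analysis rule for the CSF MMRM: "Data from early discontinuations will also be included". The first bullet of Section 9.7.1.6.3 repeats it for Aβ(1-40) and the BACE1 variables. Section 9.7.1.8.3 defines a last on-treatment value for laboratory parameters; no such definition is given for CSF.

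**The concern.** The scheduled samples share one condition: a few hours after a dose, at steady state. An ED sample from a subject who has already stopped is taken under another: no dose that day, and up to a week since the last one. The protocol's own PK/PD model (Sections 9.1 and 9.4.4) ties CSF reduction to plasma concentration, so the effect in such a sample should have partly faded. Entering it in the MMRM beside on-drug values mixes washout into an estimate labelled as the reduction during treatment. Placebo values are not affected, so the error runs one way: the active arms look less effective than they are on drug. With about 15 subjects per arm and voluntary CSF consent, a few such samples could matter.

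**Working it through.** **Inputs from the protocol**
- Table 3 (Section 9.4.4), for 5/15/50 mg: average steady-state concentration 3.3/10/33.5 ng/mL; 24-hour AUC 80.3/240.9/803.0 ng·h/mL; predicted CSF Aβ(1-x) reduction 33/56/79%.
- Longest planned gap between last dose and ED visit: 7 days (Table 7 footnote b).
- PK steady state reached within the first 2 weeks. This appears only in a rationale in the Amendment 04 revision history and is used here only to bound the half-life.

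**Assumptions, not in the protocol**
- Steady state takes 4 to 5 half-lives, so the half-life is at most 14/5 = 2.8 to 14/4 = 3.5 days. A 1-day half-life is shown as a faster case.
- CSF effect follows plasma concentration without delay.
- 20% of an arm's samples at the analysed time are off-drug ED samples. No dropout or CSF consent rate is stated.

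**Step 1. Check Table 3.** AUC/24 = 3.35/10.04/33.46 ng/mL, which agrees with the stated averages.

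**Step 2. Concentration-effect curve.** Fitting R(C) = 100·C^h / (EC50^h + C^h) to the three dose levels gives EC50 = 7.5 ng/mL and h = 0.88. The curve returns 32.8/56.3/78.8% against the stated 33/56/79%.

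**Step 3. Effect d days after the last dose.** C(d) = C(0) × 0.5^(d / half-life). At 2.8 days, the fraction of concentration left is 0.781 after 1 day, 0.476 after 3 days and 0.177 after 7 days. Putting these into R gives (5/15/50 mg):

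| Half-life | 1 day off | 3 days off | 7 days off |
|---|---|---|---|
| 3.5 days | 29.1/51.9/75.7% | 22.5/43.3/68.8% | 12.6/27.5/52.3% |
| 2.8 days | 28.2/50.9/74.9% | 20.3/40.1/65.9% | 9.6/21.9/44.7% |
| 1 day | 21.0/41.1/66.9% | 7.3/17.1/37.3% | 0.7/1.8/4.9% |

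**Step 4. Bias in an arm's mean.** Bias = share × (on-drug reduction − off-drug reduction). With a 20% share and a 2.8-day half-life:
- 1 day off: 0.2 × (33 − 28.2) = 1.0; 0.2 × (56 − 50.9) = 1.0; 0.2 × (79 − 74.9) = 0.8 points.
- 7 days off: 0.2 × (33 − 9.6) = 4.7; 0.2 × (56 − 21.9) = 6.8; 0.2 × (79 − 44.7) = 6.9 points. The means become 28.3/49.2/72.1%.

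Halving the share halves these figures. A shorter half-life raises them: at 1 day, the same formula gives 2.4/3.0/2.4 points after 1 day off and 6.5/10.8/14.8 after 7. The 7-day column puts every affected sample at the longest planned gap, so it is the upper end for each half-life.

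This is a simple mixture, not the MMRM itself. If the model estimates by visit, the share applies at the visit to which ED samples are assigned.

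**The case against.** **The sentence covers valid data too.** It takes in Visit 7 samples from subjects who stop later, and ED samples from subjects still being dosed at the clinic. That stands, and those data should stay in. But the sentence does not separate them from off-drug samples, and footnote v shows that off-drug samples will exist.

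**Visit windows belong in the SAP.** In general they do. Here, though, the protocol itself prescribes inclusion, so a later restriction would have to narrow a rule already fixed.

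**Few samples may be affected.** Footnote v also says "The CSF sample will not be taken at the ED Visit if this visit occurs within 3 months of a previous CSF sample". Subjects who stop within about 3 months of the Baseline or Visit 7 LP therefore give no ED sample, and the Week 4 estimate is hardly touched. Seven days is a maximum, and after one day the loss is small. All of this stands and limits the size.

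**The washout model is assumed.** The protocol does not call the inhibition reversible, and gives no half-life or CSF recovery time. That stands: the direction follows from the protocol's own concentration-effect model, but the size does not.

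**A treatment-policy analysis could use off-drug data.** It would need values at the planned time whether or not the subject was still on drug. Table 7 schedules no CSF in follow-up, so an ED sample is neither an on-treatment value nor an 18-month value.

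**Conclusion.** The point holds. As written, the rule admits off-drug ED samples to an analysis of the reduction during treatment and biases the active arms toward zero, mainly after Week 4. At a 2.8-day half-life with 20% of samples affected, the bias runs from about 1 point (1 day off) to about 5 to 7 points (7 days off). Half-life, CSF recovery time, dropout and CSF consent rates are all unstated, so these figures illustrate and do not estimate.

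A reader might infer three stronger conclusions, which the protocol does not support:
- **More bias at the highest dose through more stopping.** Section 9.4.4 reports no infection or drug rash at 100 mg or below in Study 002 and expects 50 mg here to be similar or better. Differential stopping is not established.
- **A flattened dose-response.** At 2.8 days and 7 days off, the losses of 4.7/6.8/6.9 points narrow the 5-to-50 mg spread only from 46 to about 44 points. Complete loss of effect with the same share would narrow it more (26.4/44.8/63.2%, a spread of 36.8), but nothing in the protocol shows which case applies.
- **A wrong Phase 3 dose.** Sections 9.1 and 9.4.4 evaluate the doses by mean and median change at 4 weeks or later and by PK/PD modelling. The MMRM is not named for that purpose.

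**What to change.** Add one sentence to Section 9.7.1.6.2 and to the first bullet of Section 9.7.1.6.3. The main CSF MMRM keeps every on-drug sample from subjects who later discontinue, including Visit 7 samples and ED samples from subjects still being dosed. It excludes ED samples taken more than a stated interval, for example 24 hours, after the last dose. Report a sensitivity analysis that includes all ED data, and use the excluded samples in the exposure-response modelling already planned in Section 9.7.1.7.2, with the PK sample that Table 7 footnote t requires close to the LP.

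The cost is slightly fewer observations in the main model. No visit, sampling or treatment rule changes.
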